9.10.4. Post-discharge methods

- a.** A home visit will be made by an investigator on the day of or day after discharge. The investigator will:
- i. Ensure the equipment is set up correctly and reinforce the previous training on myAIRVO 2. (Appendix 1).
 - ii. Check participants will have the myAIRVO 2 user manual and the 'Patient summary sheet' as an easy reference for device use.
 - iii. Perform lung function tests using a spirometer (Jaegar pneumotac spirometer with J-Lab software) according to ATS/ERS Taskforce standards.^{10 11} Participants will not be required to withhold bronchodilator medication prior to testing. The drug, dose and time of the last administration prior to spirometry will be recorded. This will inform COPD severity of participants and baseline lung function measurements.
- b.** Participants on domiciliary oxygen will have oxygen saturations recorded on simple nasal prongs according to their existing prescription. NHF therapy will then be initiated and oxygen will be titrated through myAIRVO 2 to determine the flow of oxygen delivery required to achieve the same oxygen saturation level (Section 9.10.04).

c. myAIRVO 2 devices will electronically record data on the date and time the device was used. Should participants change the flow of their myAIRVO 2 device (participants without domiciliary oxygen only) or alter the temperature, they will be asked to document this in their diary.

d. On the 3rd, 7th, 14th and 21st and 28th day post discharge the investigator will contact the participant by phone. Participants will be asked:

- i. If they are having any problems using myAIRVO 2.
- ii. If they have needed to return to the hospital, the reason and length of their hospital visit. These details will be checked against hospital records. In addition, they will be asked if they have needed to visit their GP or other allied health care practitioners and the reason. The Investigator will complete the CRF and the medical history log, concomitant medications log, medical contact log, adverse event/ serious adverse event forms as required.

e. On the 31st day post discharge an investigator will perform a home visit or the participant will visit the study investigator at their clinic office.

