- i. When the investigator contacts the participant on day 28th day post discharge they will confirm with the participant the home /office visit time on the 31st day post discharge and that their last period of myAIRVO 2 use is to commence on day 30 (the day before the home/office visit).
- ii. At the home/office visit the NHF therapy Questionnaire will be administered.
- iii. Participants will be asked whether they have had any hospital admissions and the length and cause for any admissions. These details will be checked against hospital inpatient records. In addition they will be asked if they have visited their GP or other allied health care practitioners. The Investigator will complete the CRF and the medical history log, concomitant medications log, medical contact log, adverse event/ serious adverse event forms as required.
- iv. Lung function will be performed using a spirometer (Jaegar pneumotac spirometer with J-Lab software) according to ATS/ERS Taskforce standards.^{10 11} Participants will not be required to withhold bronchodilator medication prior to testing. The drug, dose and time of the last administration prior to spirometry will be recorded. This will inform if lung function has improved during the study.
- v. The myAIRVO 2 device and associated equipment will be collected from the participant.

9.10.5. myAIRVO 2 domiciliary oxygen assessment and prescription

a. The participant will have their prescribed domiciliary oxygen flow rate recorded.

b. Oxygen saturation levels will be measured (Point A) by oximetry after at least 5 minutes at rest using standard nasal prongs with oxygen administered according to their prescription (Flow A). Should the participant's oxygen saturation levels be <88% or ≥95% they will be withdrawn from the study and referred for review of their home oxygen prescription.

c. NHF therapy will then be administered to the participant by myAIRVO 2 set at a flow rate of 25L/minute with supplemental oxygen delivered at Flow A for at least 5 minutes whilst the participant is at rest. Oxygen saturation levels will then be recorded.

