d. While myAIRVO 2 is delivering 25L/min flow, oxygen will be titrated via the device by 0.5L/min every 5 minutes until the oxygen saturation levels measured at Point A (i.e. with the portable oximetry probe after sitting at rest for at least 5 minutes using standard nasal prongs with oxygen administered at Flow A) are equivalent. This flow rate will be used for supplemental oxygen delivered during NHF therapy via myAIRVO 2 throughout the study period.

e. An explanation will be given to the participant in respect to the risks and symptoms of hyperoxia, hypoxia, and hypercapnea, how to use myAIRVO 2 with correct oxygen flow rates, and how to change the oxygen flow between myAIRVO 2 and their standard nasal prongs (if required). They will also be provided with the “Quick guide sheet’ specific to patients on domiciliary oxygen.

f. If there is any clinical concern, the participant will be withdrawn from the study at the Investigator’s discretion. This may include, but is not limited to, concern regarding ability to maintain oxygen saturations within a safe range, the participant’s ability to understand the risks and symptoms of hypercapnia and hypoxia, and the participant’s ability to administer oxygen safely within the prescribed regimen.

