9.11. Withdrawal Criteria

Participants are able to stop the intervention at any time, without being withdrawn from subsequent portions of the study. Participants may withdraw from the entire study at any time without giving a reason. Participants may be withdrawn at the discretion of the Investigator for any reason that is believed may present a safety risk.

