11.6. Selection Criteria

For endpoint details see section 9.4. All participants who were screened to take part in the study will be included in the analysis of endpoint 2.b.i. All patients who were discharged with a myAIRVO 2 device to take home will be included in analysis of all other endpoints.

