12.3. Reporting Adverse Events

For the purposes of this study the following events will be considered to be serious adverse events (SAEs):

- Death
- Life-threatening event

- Permanently disabling or incapacitating event
- Hospitalisation or prolongation of hospitalisation. Hospitalisation for the purposes of SAE reporting is defined as an admission to hospital and does not include a presentation to the ED followed by discharge without admission or an admission for elective reasons
- Any event considered serious by the study investigator

SAEs will be reported to the Sponsor (Fisher and Paykel Healthcare) within 24 hours of the investigator becoming aware of the event on the study SAE form. Other adverse events will also be reported to the Sponsor within seven days.

Other adverse events (AEs) will be reported to the Sponsor (Fisher and Paykel Healthcare) within 7 days of the investigator becoming aware of the event on the study AE form.

Device deficiencies (related to the identity, quality, durability, reliability, safety or performance of a device) will be reported to the Sponsor (Fisher and Paykel Healthcare) in writing. If the investigator deems the event could have led to a serious adverse event, it must be reported within 24 hours of the investigator becoming aware of it, otherwise it should be reported within 7 days. The sponsor will manage device deficiency reports as part of its ongoing post marketing safety review process and the investigator will supply the sponsor with additional safety information as required.

Adverse events and device deficiencies will be reported to the HDEC, IRB, Medsafe and FDA as required

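### When the investigator acts for safety, the plan offers only withdrawal and states no continued follow-up, although those who stop the device by choice stay in the study

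*Combined protocol and SAP*

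**What the plan says.** Section 9.11 distinguishes leaving the device from leaving the study when the decision is the participant's: "Participants are able to stop the intervention at any time, without being withdrawn from subsequent portions of the study". For an investigator acting on safety, the text speaks only of withdrawal:

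- **9.10.5f** (home-oxygen users, after titration on NHF): "If there is any clinical concern, the participant will be withdrawn from the study". The sentence goes on to make this a matter for the investigator's discretion.
- **9.10.5b** (home-oxygen users, saturation outside the stated limits on their usual prongs): "they will be withdrawn from the study and referred for review of their home oxygen prescription". No discretion is stated.
- **9.10.3f** (the same test in hospital, where possible): the same mandatory wording.
- **9.11** (all participants): "Participants may be withdrawn at the discretion of the Investigator for any reason that is believed may present a safety risk". This is permissive and does not say what the participant is withdrawn from.

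The analysis set in 11.6 makes no exception for later withdrawals: "All patients who were discharged with a myAIRVO 2 device to take home will be included in analysis of all other endpoints". The only endpoint treated differently there concerns screening.

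Readmission, GP and adverse event data are gathered at the phone calls on days 3, 7, 14, 21 and 28 and at the day-31 visit (9.10.4d and e). The calls ask: "If they have needed to return to the hospital, the reason and length of their hospital visit. These details will be checked against hospital records".

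**The concern.** A participant who gives up the device by choice and one whose device is stopped for safety both bear on objective 5, which is to estimate readmission, ED and GP visit rates for the planned trial. The plan gives only the first a written route to stay in follow-up. If withdrawal is applied as worded, the second has no stated calls, day-31 contact, record check or adverse event forms, but remains in the 11.6 denominator if discharged with a device.

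Two things are at stake. First, outcomes may be missing for a reason related to the participant's risk, and no analysis can recover what was not collected. Second, section 8.4 names hyperoxemia, carbon dioxide retention and hypoxemia as risks for participants on supplemental oxygen. If follow-up ends when an investigator becomes concerned about such a participant, harm appearing later may go unseen.

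**Working it through.** **Step 1: the plan's own figure.** Section 11.2 requires at least 80 patients and expects 20% drop-out: 80 / (1 − 0.20) = 100, which matches the stated total. The 20% covers all causes; no share is given for safety withdrawals.

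**Step 2: the clauses side by side.**

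| Situation | Who | Discretion | Stated consequence |
|---|---|---|---|
| Stops by choice (9.11) | all | participant's | stays in the later parts of the study |
| Saturation limits in hospital (9.10.3f) | oxygen users | none stated | withdrawn from the study |
| Saturation limits at the oxygen assessment (9.10.5b) | oxygen users | none stated | withdrawn from the study |
| Clinical concern (9.10.5f) | oxygen users | investigator's | withdrawn from the study |
| Safety risk (9.11) | all | investigator's | may be withdrawn |

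No row lets the investigator stop the device and keep the participant in follow-up.

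**Step 3: handling in the analysis.** Section 11.1 describes the readmission, ED and GP proportions by numbers and percentages, with no rule for an unknown outcome. It names Poisson regression for visit counts without saying how shortened follow-up enters. Its censoring sentence covers people not admitted within study time and does not mention withdrawal.

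**Step 4: illustration of size.** From the documents: 30-day readmission p = 21% (USA, all readmissions, section 7.2) and N = 100. Assumed, because the documents give neither: w participants withdrawn at day 0 or 1 without follow-up, and their relative readmission risk R.

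- Rate in all 100 = [(100 − w) × p + w × R × p] / 100
- Estimate if the withdrawn are censored at once: about p = 21%
- Estimate if they are counted as event-free: (100 − w) × p / 100

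With R = 2:

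| w | Rate in all 100 | Censored | Counted event-free |
|---|---|---|---|
| 5 | (19.95 + 2.10)/100 = 22.05% | 21%, low by 1.05 points | 19.95%, low by 2.10 points |
| 10 | (18.9 + 4.2)/100 = 23.1% | 21%, low by 2.1 points | 18.9%, low by 4.2 points |

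Sensitivity to the assumptions:

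- R = 1: the rate in all 100 is 21%, so censoring gives no bias. Counting as event-free is still low, by 1.05 points (w = 5) or 2.1 points (w = 10).
- R = 0.5, w = 10: (18.9 + 1.05)/100 = 19.95%, so censoring is 1.05 points too high. The direction is therefore not fixed.
- p = 8% (New Zealand, AECOPD readmissions), R = 2: the rate in all 100 is 8.4% (w = 5) or 8.8% (w = 10), so censoring is low by 0.4 to 0.8 points.

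**Step 5: bounds that assume no R.** With k readmitted among those followed, the proportion in all 100 lies between k/100 and (k + w)/100.

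- w = 5, k = 20 of 95: 20% to 25%
- w = 10, k = 19 of 90: 19% to 29%
- w = 20 (the whole drop-out allowance, an extreme case), k = 17 of 80: 17% to 37%

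**Step 6: comparison with sampling error.** The 95% half-width for 21% with n = 100 is 1.96 × √(0.21 × 0.79 / 100) = 0.080, or about 8 points.

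**The case against.** A reader might infer more than the documents support, and several points on the other side stand.

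- **That any safety concern automatically ends participation.** It does not: 9.10.5f is discretionary, 9.11 is permissive, and only the saturation rules in 9.10.3f and 9.10.5b are mandatory. But discretion governs whether to withdraw. It does not supply a device-only route.
- **That those withdrawn are the highest-risk participants.** The documents give no risk for this group. The 9.10.5b test is made on ordinary prongs, before NHF is started at that visit, and it also catches saturations of 95% and above. Two of the three examples in 9.10.5f concern understanding and safe administration of oxygen. Prior exposure remains possible, because 9.10.2b starts the intervention in hospital and Appendix 2 expects a period of NHF use there.
- **That outcomes and SAEs are lost.** This would be an inference from silence. Section 12.3 says "SAEs will be reported to the Sponsor (Fisher and Paykel Healthcare) within 24 hours of the investigator becoming aware of the event", sets no stop at withdrawal, and hospital records are a named source. The text just before 12.2 and the data collection SOP were not available for review. Still, records serve to check what participants report, no record source is named for GP visits, and scheduled contact is the main written route by which an investigator would become aware of events.
- **That everyone affected is in the analysis set.** Those withdrawn in hospital under 9.10.3f may never enter it. Because 9.10.3g allows the device to be brought to the home after discharge, membership is unclear for some others.
- **That the rates are biased low.** This depends on assumed counts and an assumed doubled risk. The plan contains no rule counting withdrawn participants as event-free.

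It is also fair that this is a single-arm feasibility study with no pass/fail criteria, that readmission is a secondary outcome, and that withdrawals and their reasons are already endpoints. These points lower the weight of the gap without closing it.

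**Conclusion.** The gap is in the text. An investigator who acts for safety has no written way to stop the device and keep following the participant, no available passage provides for data collection after such a withdrawal, and 11.6 still counts those discharged with a device. Readmission, ED and GP outcomes may therefore be missing for reasons related to risk, and harm after NHF exposure may go unseen.

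The direction and size of any bias cannot be established from the documents. Under the stated illustration, the shortfall with censoring is well inside the sampling error of about 8 points. The case for change rests mainly on collecting safety and outcome data that cannot be recovered later. Severity is minor to moderate. No view is taken on the clinical criteria for withdrawal.

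**What to change.** Leave the clinical criteria and the referral as they are.

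1. In 9.10.5b, 9.10.5f and the safety sentence of 9.11, state that stopping the device for safety does not itself end study follow-up. For participants discharged with a device, the scheduled calls, hospital-record check, day-31 contact and AE/SAE reporting continue to day 31 unless consent is withdrawn.
2. Reconcile 9.10.3f and 11.6 with this wording, so that the same saturation finding in hospital and at home does not leave follow-up status unclear. State in 11.6 how a participant whose device is brought to the home after discharge is classed.
3. State in 11.1 how participants who do leave the study enter the denominators and the censoring.
4. Record device discontinuation and study withdrawal separately on the enrolment and withdrawal log.

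The cost is protocol wording plus contacts that are already scheduled. The small downside is a few extra contacts with participants who no longer use the device.

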9.10.6. Excluded participants

All participant exclusions will be documented on the Participant eligibility_screening log

9.10.7. Associated documents

Documents associated with this methodology include:

1. Consent form and participation information sheet for New Zealand participants
2. Consent form and participant information sheet for USA participants
3. Case report forms:
 - a. CRF NZ
 - b. CRF US
 - c. Medical history log
 - d. Concomitant medications log
 - e. Adverse event (AE) form
 - f. Serious adverse event (SAE) form
 - g. Medical contact log
4. NHF therapy diary oxygen
5. NHF therapy diary no oxygen
6. NHF therapy questionnaire
7. Participant eligibility_screening log
8. Participant enrolment_withdrawal log
9. Fisher and Paykel myAIRVO 2 user manual
10. Patient summary sheet oxygen NZ
11. Patient summary sheet oxygen US
12. Patient summary sheet no oxygen NZ
13. Patient summary sheet no oxygen US
14. Data collection SOP
15. myAIRVO 2 electronic monitoring SOP
16. Equipment provision SOP
17. Equipment log
18. LACE Index

9.11. Withdrawal Criteria

Participants are able to stop the intervention at any time, without being withdrawn from subsequent portions of the study. Participants may withdraw from the entire study at any time without giving a reason. Participants may be withdrawn at the discretion of the Investigator for any reason that is believed may present a safety risk.

9.12. Number of Trial Subjects

100 (20 from NZ and 80 from USA sites, respectively) subjects.

9.13. Follow up Plan

The device will be used for 30 days at home post discharge of AECOPD. Participant contact by phone will occur on the 3rd, 7th, 14th and 21st and 28th day post discharge to check whether the participant has any problems

using myAIRVO 2. At the end of the 30 days a further home visit or office visit (participant preference) will occur, a questionnaire will be administered and the device collected. Participants are also able to contact investigators during the study period by phone for assistance. When study visits and phone calls fall outside of the working week these should be rescheduled to take place +/- 1 day of the specified date.

The level and duration of follow up should permit the demonstration of performance over a period of time sufficient to represent a realistic test of the protocol and the myAIRVO 2 device.

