7.5. Justification for Administration

Participants will be asked to use myAIRVO 2, for participants on domiciliary oxygen, the oxygen will be delivered via the device (see section 9.10.04). Participants will not be given a specific time period to wear the device, but encouraged to use the therapy every day as much as possible without impacting on their daily routines. The first day after discharge will be classed as day one of the study. NHF therapy will be monitored from day one for a period of 30 days.

For all participants NHF therapy will be initiated at 25L/min with a the temperature setting of 37°C. All participants have the ability to reduce the temperature setting to 34°C. In participants who are not prescribed oxygen there will be the further option to increase or decrease flow rates (up to 30L/min or down to 20L/min). These modifications are to assist with comfort and adherence. Patients who are prescribed domiciliary oxygen flow rates will remain constant to deliver a more consistent concentration of oxygen.

The outcomes of this study will inform the appropriate methodology for subsequent randomized control trials to investigate the efficacy of NHF therapy in the long-term management of COPD patients. Given this, therapy settings, compliance to the therapy in this feasibility study are modifiable to gain maximum understanding of therapy usage.

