9.4. End Points

The following end points will be evaluated:

Primary outcome:

The primary outcome will be NHF use for 30 days following discharge after AECOPD. Use will be expressed as hours of myAIRVO 2 use per day over 30 days, as obtained by myAIRVO 2 electronic monitoring.

Secondary outcomes:

Other use variables:

- i. Number of days of use, adjusted for number of days with myAIRVO 2 at home
- ii. Average use per day of myAIRVO 2 during week 1, week 2, week 3 and week 4.
- iii. Average use per day on days of myAIRVO 2 use

Withdrawals and exclusions:

- i. Proportion of participants screened that were excluded
- ii. Reason for exclusion
- iii. Proportion of participants enrolled that were withdrawn
- iv. Reason for withdrawal

Participants requiring oxygen delivery via myAIRVO 2:

- i. Proportion of participants using domiciliary oxygen

Aspects of myAIRVO 2 use:

- i. Proportion of participants who reported having reduced myAIRVO 2 flow settings from the initial flow
- ii. Reduction in flow
- iii. Proportion of participants who reported having increased myAIRVO 2 flow settings from the initial flow
- iv. Increase in flow
- v. Proportion of participants who reported having reduced myAIRVO 2 temperature setting from the initial setting
- vi. NHF therapy Questionnaire results

Clinical outcomes

- i. Proportion of participants with at least one hospital readmission within 30 days of discharge
- ii. Reasons for hospital admissions (AECOPD, other respiratory cause or other cause)
- iii. In those that had at least one hospital readmission:
 - a. Number of readmissions
 - b. Time to first hospital readmission
 - c. Hospital readmission length
- iv. Proportion of participants with at least one ED visit within 30 days of discharge
- v. Reason for ED visits (AECOPD, other respiratory cause or other cause)
- vi. In those that had at least one ED visit:
- vii. Number of ED visits
- viii. Time to first ED visit
- ix. Proportion of participants with at least one GP visit within 30 days of discharge
- x. Reason for GP visits (AECOPD, other respiratory cause or other cause)
- xi. In those that had at least 1 GP visit within 30 days of discharge: number of GP visits
- xii. LACE Index for hospital admissions
- xiii. Lung function measurements (FEV₁, SVC_{in} and FVC) at day 1 and 31.

* An ED visit is counted if the patient went to ED for assessment and was not subsequently admitted to a hospital ward.

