9.10.2. Interventions

a. Participants will be split into 2 groups (those on a domiciliary oxygen prescription at the time of study entry and those who are not) with both groups receiving NHF therapy by myAIRVO 2. Participants will be encouraged to use myAIRVO 2 as much as possible (day and night) each day without impacting on daily living activities. Participants who are prescribed domiciliary oxygen will use NHF therapy via myAIRVO 2 with supplemental oxygen delivered via the device (section 9.10.04).

b. Interventions will be initiated from the time the participant is enrolled in hospital, to aid familiarization and acclimatization, and used until 30 days following discharge. Note the day of discharge is defined as Day 0.

c. By default, NHF will be set at 25L/min at 37°C. However, all participants are able to lower the delivered temperature to 34°C. For participants without a domiciliary oxygen prescription they can also increase/decrease the flow rate (up to 30L/min or down to 20L/min). Participants who have domiciliary oxygen flow rates are fixed in order to deliver a more consistent concentration of oxygen to maintain oxygen saturation.

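### The +/- 1 day weekend rule puts some closing visits on day 30, in conflict with the last use period and the 30-day endpoint windows (minor)

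*Combined protocol and SAP*

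**What the plan says.** **Day count.** Section 9.10.2b: "Note the day of discharge is defined as Day 0". Section 7.5: "NHF therapy will be monitored from day one for a period of 30 days". The observation window is therefore days 1 to 30.

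**Closing visit.** Section 9.10.4e: "On the 31st day post discharge an investigator will perform a home visit", or the participant attends the clinic office instead. Under item v of the same list, "The myAIRVO 2 device and associated equipment will be collected from the participant". At the day-28 call (item i) participants are told that "their last period of myAIRVO 2 use is to commence on day 30 (the day before the home/office visit".

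**Rescheduling.** Section 9.13 covers study visits and phone calls together. Those that "fall outside of the working week these should be rescheduled to take place +/- 1 day of the specified date". The shift may go in either direction, and the closing visit is not treated separately.

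**Endpoints.** Section 9.4, primary outcome: "Use will be expressed as hours of myAIRVO 2 use per day over 30 days". Among the clinical outcomes: "Proportion of participants with at least one hospital readmission within 30 days of discharge", with matching 30-day proportions for ED and GP visits.

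**Analysis.** Section 11.1 permits, but does not require, weighting of the mean for time in the study. No section says how a closing visit on day 30 or day 32 is handled.

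**The concern.** A symmetric one-day shift does no harm to a phone call. The closing visit is different, because it ends device recording and is the last planned contact for events. If it moves back to day 30, the device is collected on the day the last use period is due to begin. A participant who mainly uses the device overnight would then have no day-30 period at all. Questions about hospital, ED and GP contacts would also be asked before day 30 is over.

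The weekday of discharge determines who is affected, so the conflict can be foreseen at enrolment. A site that meets it must depart from either the visit window or the last-use instruction, and the protocol does not say which. The study is meant to inform the procedures of a later randomized trial, so the conflict could be carried forward.

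**Working it through.** **Inputs from the documents.** Discharge is day 0 (9.10.2b). The closing visit is on day 31 (9.10.4e). The permitted shift is +/- 1 day (9.13). The window is 30 days (9.4). N = 100 (9.12). Readmission figures are 8% at 30 days for AECOPD in the New Zealand audit and 21% at 30 days in the USA (7.2).

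**Assumptions.** The working week is Monday to Friday; the protocol does not define it. The documents give no pattern of discharge weekdays, so two are used: even over seven days, and weekdays only.

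**The plan's own figure.** 80 / (1 - 0.20) = 100, as in 11.2. The point does not depend on it.

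**Step 1, calendar.** 31 = 4 x 7 + 3, so day 31 falls three weekdays after the weekday of discharge.

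| Discharge (day 0) | Day 31 | Working days within +/- 1 | Visit held |
|---|---|---|---|
| Monday | Thursday | not needed | day 31 |
| Tuesday | Friday | not needed | day 31 |
| Wednesday | Saturday | Friday only (Monday is +2) | **day 30** |
| Thursday | Sunday | Monday only (Friday is -2) | **day 32** |
| Friday | Monday | not needed | day 31 |
| Saturday | Tuesday | not needed | day 31 |
| Sunday | Wednesday | not needed | day 31 |

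**Step 2, share moved to day 30.** Even over seven days: 1/7 = 14.3%, or about 14 of 100. Weekdays only: 1/5 = 20%, or 20 of 100. With 80 participants and 1/7, the chance that at least one is affected is 1 - (6/7)^80, above 99.99%. Under the same assumptions an equal share moves to day 32.

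**Step 3, effect on the primary mean.** Take a participant who uses the device u hours every day and loses all of day 30.
- Fixed 30-day denominator: 29u/30, a loss of 1/30 = 3.3%. Over the cohort this is (1/7) x 3.33% = 0.48%, or (1/5) x 3.33% = 0.67%.
- Denominator of days with the device: 29u/29 = u, no loss.

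The first result is an upper bound, because some day-30 use may be recorded before the visit.

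**Step 4, effect on an event proportion.** Suppose the hazard is constant and nothing on day 30 is recovered. The 29-day risk is then 1 - (1 - p)^(29/30).
- p = 8%: 7.74%, a difference of 0.26 percentage points. Over the cohort: 0.26 x 1/7 = 0.04 to 0.26 x 1/5 = 0.05 points.
- p = 21%: 20.38%, a difference of 0.62 points. Over the cohort: 0.62 x 1/7 = 0.09 to 0.62 x 1/5 = 0.12 points.

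In 100 participants this is roughly a tenth of an event at most.

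**The case against.** The strongest reply is that nothing the study informs would change. The study has one arm and no pass/fail criteria. As an illustration with assumed values, take mean use of 4 to 8 hours per day, a standard deviation of 2 to 4 hours and n = 80. The loss is then about 1 minute (0.48% of 4 h) to 3 minutes (0.67% of 8 h) per day. The 95% half-width is 1.96 x 2/√80 = 0.44 h to 1.96 x 4/√80 = 0.88 h, or 26 to 53 minutes. This stands, and it is why the point is minor.

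A reader might infer that the error runs one way, towards lower use and missed events. The documents do not support that:
- The primary outcome is a rate, and its denominator is not fixed at 30. Section 11.1 allows weighting for time in the study, and the number of days of use is adjusted for days with the device at home (9.4).
- If use declines over the month, dropping the last day raises the average.
- Thursday discharges keep the device a day longer.
- Reported admissions are checked against hospital records (9.10.4), and unplanned admissions are reportable as SAEs (12.3).

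What remains is narrower. No record check is stated for GP visits. Section 9.4 counts an ED visit only when no ward admission follows, so the inpatient-record check at closing would not clearly find one.

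It can also be said that 9.13 uses should rather than must, that the visit time is agreed at the day-28 call, and that the protocol already allows a day's slack for home set-up after discharge. These soften the conflict but do not remove it: the same day-28 call carries the instruction that cannot be met.

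**Conclusion.** This is a minor but genuine inconsistency between two stated rules. Given a Monday-to-Friday working week, every Wednesday discharge has its closing visit moved to day 30. That contradicts 9.10.4e.i and cuts short the 30-day windows in 9.4. For Thursday discharges the visit falls on day 32; the window is complete, but day 30 is no longer the day before the visit.

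The size is small. The 14% to 20% share rests on assumed discharge weekdays. The loss in the primary mean is an upper bound that needs a fixed 30-day denominator and all day-30 use lost. Only late day-30 GP visits and ED visits without admission are at real risk of being missed. A claim of material or one-directional bias in the primary outcome would go beyond the documents.

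**What to change.** 1. Reconcile 9.13 with 9.10.4e so that the closing visit and the ascertainment of events do not come before the end of the 30-day window. The date of device collection is for the sponsor to settle: 9.13 also describes 30 days of home use, and this review does not propose when treatment should end.
2. State one cut-off in 9.4 or 11.1 that applies whatever the visit date: device data count up to the use period that starts on day 30, and events count through day 30. This also deals with visits on day 32.
3. Define the primary outcome per day with the device at home within that window. Days on which the device is at home but unused count as zero. Report the number of days held alongside, because the denominator then differs for anyone who returns the device early.
4. If a visit does take place on day 30, complete readmission, ED and GP ascertainment through day 30 from records or by a phone contact.

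The cost is a few sentences of protocol wording, a data-handling rule, and possibly one short call or record check for those seen on day 30. The sample size stays at 100.
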